Study protocol and statistical analysis plan

Date: October 22, 2019

Citation:

[name], [name], [name], [name], [name], [name], [name], [name], [name], [name]. Empowering active self-management of arthritis: Effectiveness of an online self-management tool for people with rheumatoid arthritis: a research protocol. *BMC Trials*. (DOI: 10.1186/s13063-019-3851-0) 20:712, 2019.

<https://trialsjournal.biomedcentral.com/articles/10.1186/s13063-019-3851-0>

Background

Self-management is a key component of successful chronic disease management [1]. Broadly, it is a process where patients are actively participating in a variety of activities that contribute to lessening of the physical and emotional impact of their illness. Such activities include adhering to their treatment plan, being physically active, and seeking medical help when the treatment target is not met. It is important to make self-management a priority as patients can benefit from learning about how their daily activities and treatments correlate with their symptoms and health status on an ongoing basis. This contextualized health data provides a baseline for patients to determine if their symptoms warrant seeking medical attention and could inform their decisions about daily activities. For example, a patient who is aware of how much pain and fatigue they experience following a day of housework will know to pace their activities the next day.

Chronic disease self-management is hard work; it can be difficult to follow treatment regimes in the context of busy lives and fluctuating symptoms. There is a need to develop a multifaceted approach that can promote self-management and adherence to recommended treatments. As an example, for people with RA, there is ample evidence to support early and persistent use of disease-modifying anti-rheumatic drugs (DMARDs) [2]. However, for people who started RA medications, the adherence rates are as low as 30% [3]. Furthermore, despite the compelling evidence supporting a physically active lifestyle in reducing symptoms [4-7], the majority of patients do not meet the minimum recommended level of moderate-to-vigorous physical activity (MVPA) [8].

In general, patients feel a moral obligation to “manage well” [9]. However, some become disengaged from self-management activities [10] because of a frustration from managing their

health on a trial-and-error basis [11]. The current practice relies on patients applying their self-management knowledge and skills in daily life with little feedback on their performance or how their actions affect their health. In light of these findings, we believe that there is a need for a multifaceted approach that provides support in terms of knowledge, skill development and timely advice from health professionals, as well as motivational support for patients to be engaged in their care and to stay physically active.

OPERAS web application

The OPERAS web app was designed to engage patients in monitoring and managing their health. Building from two existing software programs, the Arthritis Health Journal (AHJ) [12] and FitViz [13], OPERAS allows users to track symptoms, self-management goals, medication use, and physical activity. The latter is automatically measured by Fitbit. Using OPERAS, a physiotherapist (PT) will provide remote counselling to guide the user in setting realistic physical activity goals. Based on the users' goals, the PT can adjust parameters of physical activity intensity and duration to provide automated personalized feedback on their goal attainment.

The objectives of this study are to: 1) assess the efficacy of OPERAS at improving self-management ability of people with RA in a 6-month randomized controlled trial (RCT); 2) explore the effect of OPERAS on disease status, pain, fatigue, depressive symptoms, and characteristics of habitual behavior; and 3) assess barriers to implementation and sustainability of OPERAS from the perspectives of participants involved in the study.

Methods/design

Study Design

The *Empowering active self-management of arthritis: Raising the bar with OPERAS (an On-demand Program to Empower Active Self-management)* project will use a mix of quantitative and qualitative research methods. The RCT will employ a delayed control design, whereby participants will be randomly assigned to start the 6-month intervention immediately (Immediate Intervention [II] group) or 6 months later (Delayed Intervention [DI] group) using a 1:1 allocation ratio. Participants will be assessed 3 times throughout the study (Fig. 1.). At the end of the intervention, we will invite a sample of participants to be interviewed regarding their experiences.

Participants

Individuals are eligible for the study if they have: 1) a rheumatologist confirmed diagnosis of RA; 2) no joint surgery in the past 6 months; 3) no history of acute injury to any joints in the past 6 months; 4) an email address and daily access to a computer or mobile device; 5) the ability to speak and understand English; and 6) not previously participated in studies involving the AHJ or physical activity counselling. We will exclude people who should not be physically active without medical supervision, as identified by the Physical Activity Readiness Questionnaire (PAR-Q) [14]. If participants fail the PAR-Q, a physician's note will be required to determine if they are eligible.

Participants will be recruited from rheumatology clinics in Metro Vancouver, and through the network of patient groups including Arthritis Consumer Experts, and Arthritis

Research Canada's Arthritis Patient Advisory Board. We will also post study information in social media (Facebook, Twitter, Kijiji, Craigslist) and Arthritis Research Canada's website.

Once participants complete the screening process and are deemed fully eligible for the study, the study coordinator will provide detailed information on the study, and a consent form will be emailed to the participant. When a signed consent form is obtained (e-signature or scanned copy), the participant will be enrolled. All potential and consented participants will be assigned a study ID which links to their personal and contact information. This information will be stored in a password-protected file on a secure database only accessible to the research team.

STUDY PERIOD					
	Enrolment	Baseline	Post-allocation		
Weeks	-1 to 0	0 (T0)	1	27 (T1)	53 (T2)
ENROLMENT:					
Eligibility	X				
Informed consent	X				
Allocation		X			
INTERVENTIONS:					
Immediate Group (N= 67)					
Education Session			X		
Access to OPERAS web-app and Fitbit (Weeks 1-53)					
PT Phone Calls (Weeks 2- 26)					
Delayed Group (N=67)					
Education Session				X	
Access to OPERAS web app and Fitbit (Weeks 27-53)					
PT Phone Calls (Weeks 29-52)					
ASSESSMENTS:					
Patient Activation Measure (PAM)		X		X	X
Rheumatoid Arthritis Diseases Activity Index (RADAI)		X		X	X
Fatigue Severity Scale (FSS)		X		X	X
McGill Pain Questionnaire (MPQ-SF)		X		X	X
Patient Health Questoinnaire-9 (PHQ-9)		X		X	X
Self-Reported Habit Index (SRHI)		X		X	X
SenseWear Mini		X		X	X

Fig 1 Standard protocol items: recommendation for interventional trials (SPIRIT) figure

The Intervention

Participants randomized into the II group will receive the 6 month intervention immediately. They will attend a 2-hour in-person session where they will: 1) participate in a group education session from a study PT about self-management and physical activity for people with RA, 2) receive a Fitbit Flex 2 and an orientation to the OPERAS web app, and 3) receive

individual counselling from a PT trained in motivational interviewing [15]. All study PTs will follow the Brief Action Planning approach [16], whereby participants will be guided to set their own physical activity goals, develop an action plan, and identify barriers and solutions.

We will ask participants to wear the Fitbit throughout the intervention period, and use the OPERAS app to record their RA disease activity, symptoms, treatment use, and self-management action plans. If participants experience any discomfort wearing the Fitbit, we will advise them to stop wearing it but continue using the OPERAS web app. Disease activity will be tabulated from participants' self-reported measures, including the Rheumatoid Arthritis Disease Activity Index [RADAI], Visual Analogue Scale [VAS], and the Health Assessment Questionnaire [HAQ]. Participants will record their symptoms twice a week during periods of more active disease (i.e., a disease activity score above 4), and once every 2 weeks during periods of stable disease (i.e. no sudden increases in disease activity score). They will also be asked to log on and review their physical activity goal achievements at least once a week. Participants who have not recorded their disease activity for more than 2 weeks will receive an email reminder from the research team.

II participants will receive a phone call from their PTs at weeks 2, 4, 6, 8, 13 and 26 to review their physical activity goals and accomplishments. PTs will coach participants to modify their goals if they are ready.

The DI group will receive the same intervention in week 27. Participants will receive a monthly newsletter of arthritis news, which are unrelated to disease management prior to the intervention period.

After the six-month intervention period, both II and DI participants can keep the Fitbit and their OPERAS app account, but will not have access to a PT. There is no requirement for

participants to stop their medical treatments and non-pharmacological care during their participation in the study.

Measurements

All participants will be assessed 3 times throughout the study: at baseline (T0), week 27 (T1), and week 53 (T2). Baseline measurements will be completed before randomization. Research personnel performing data analysis will be blinded to the group assignment. We will not be blinding the group assignment to the study coordinator, who will be facilitating delivery of the intervention, nor the participants who will be receiving it.

Outcomes

Primary Outcome

Self-management ability will be assessed through the Patient Activation Measure (PAM), a 13-item self-reported measure of individual's confidence in managing chronic diseases [17,18]. Each item has a 4-point response, with 1 being strongly disagree and 4 being strongly agree, and the aggregate raw score is converted to 0-100 [15]. Hibbard et al [17] described a 4-stage activation model based on the standardized scores of PAM: 1) believing an active role is important (PAM score <47); 2) having confidence and knowledge to take action (47.1 - 55.1); 3) taking action (55.2 - 67); and 4) maintaining healthy behaviors despite setbacks (> 67.1). PAM has demonstrated internal consistency (Chronbach's $\alpha > 0.85$) [17], and construct validity with health status measures (e.g., SF-36 [24]) and healthy behaviours such as exercise, healthy eating and medication adherence [19].

Secondary Outcomes

We will assess disease status through the RADAI which categorizes disease activity into remission, low, moderate, and high states [20]. RADAI has 5 components, including 1) global disease activity; 2) joint tenderness/swelling; 3) pain; 4) morning stiffness; and 5) number/severity of painful joints. Its validity was supported by moderate correlations with physicians' assessment of disease activity ($r = 0.54$), swollen joint count ($r = 0.54$), and C-reactive protein value ($r = 0.43$) [18].

Pain will be measured with the McGill Pain Questionnaire (MPQ-SF), which consists of 15-pain related words that can be rated from 0 to 3, with the higher number being more severe [21]. We will measure fatigue using the Fatigue Severity Scale (FSS), a 9-item questionnaire that has demonstrated internal consistency (Cronbach's $\alpha=0.89$) [22]. The FSS is also moderately correlated with pain ($r=0.68$) and depression ($r=0.46$) [23]. We will also assess participants' mood using the Patient Health Questionnaire-9 (PHQ-9) [24] which consists of 9 questions that correspond to the diagnostic criteria for major depressive disorder. A total score of greater than 11 indicates the presence of major depressive disorder [25].

The Self-Reported Habit Index (SRHI) will be used to measure characteristics of habitual behavior. It is a 12-item scale, rated on a 7-point Likert scale, with higher scores indicating a stronger habit or behavior that is done frequently, automatically, and done without thinking about it [26, 27]. Participants will rate their strength of habit for 3 specific behaviors, including sitting during leisure time at home, sitting during usual occupational activities, and walking outside for 10 minutes or more.

We will measure participants' time spent in physical activity and sedentary activity with SenseWear Mini. It integrates tri-axial accelerometer data, physiological sensor data and

personal demographic information to estimate steps, energy expenditure and Metabolic Equivalent of Tasks (METs). Tierney et al. [28] has showed that the SenseWear is an appropriate tool in estimating energy expenditure during activities of daily living in people with arthritis (intraclass correlation coefficient (ICC) = 0.72). Participants will wear the SenseWear monitor over their triceps on the non-dominant arm for 7 days. Almeida et al [29] recommended that a minimum of 4 days is required to reliably assess energy expenditure from different levels of physical activity in people with RA (ICC > 0.80).

We will calculate: 1) the mean time spent in bouts MVPA per day. A bout is defined as ≥ 10 consecutive minutes at the level of ≥ 3 METs (i.e., the lower bound of MVPA), with allowance for interruption of up to one minute below the threshold [30]. 2) Mean daily time spent in sedentary behaviours, with an energy expenditure of ≤ 1.5 METs, occurring in bouts of > 20 minutes during waking hours [31, 32].

Implementation Assessment

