Our primary outcome measure is self-management ability as measured by the (PAM) [17,18]. In a study by Turner et al., it was reported that patients with chronic diseases who completed a 7-week self-management program would have their mean PAM score improve from

52.2 to 60.2 at 6 months (standardized effect size = 0.65) [34]. Based on a difference of 8 points, an estimated SD of 12.4, and a 2-tailed analysis of covariance (ANOVA), a total of 102 participants (51 per group) would be needed (90% power; α -level 0.05). We plan to recruit a total sample size of 134, with 67 participants in each group, to allow for a ~24% attrition rate.

For the implementation assessment, we will conduct qualitative interviews with 7-10 participants in each of the 4 purposive sampling strata, including gender (2) and experience in using health-related apps (2). Hence, 28 – 40 people will be interviewed.

Data Analysis

The data collected will be de-identified and password protected. All research personnel involved with data analysis will have access to the data files. The study coordinator will oversee the data sharing process.

Efficacy Analyses

The intervention efficacy will follow an intention-to-treat approach. We will analyze the outcomes measured at weeks 26 and 52 in the II and DI groups. We will employ Generalized Linear Mixed-effect Models (GLMM), adjusting for baseline value on the outcome variable and sex as covariates. These models are the most efficient and recommended statistical methods for analyzing longitudinal clinical trial data with missing data [35, 36] and can account for data missing at random without the need to perform explicit imputations of the missing values [37]. Binary indicators of group and months since baseline, will allow us to test their interaction ($p < 0.05$ for 2-tailed Wald test), which addresses if the outcome post-intervention is significantly better in the II than DI group. Data transformation, if needed, will be applied to continuous

outcomes to satisfy the assumption of normality. The sandwich estimators for GLMMs [38] will be used to compute empirical standard errors that are robust to model specifications and distributional assumptions. An unstructured variance–covariance matrix will be used to model the within-subject error variance-covariance for continuous outcomes. The quality of statistical inferences will be substantiated through rigorous model checking and validation techniques.

Implementation Analysis

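### At T1 only the II arm has shared education sessions and physiotherapists, and neither the efficacy model nor the 51 per arm allows for correlation between those participants.

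*Combined protocol and SAP*

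**What the plan says.** All references are to the combined protocol and SAP.

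- **The Intervention.** II participants attend one 2-hour in-person visit where they "participate in a group education session from a study PT about self-management and physical activity for people with RA" and are counselled individually by a PT. PT calls follow at weeks 2, 4, 6, 8, 13 and 26. There is more than one PT, and they share a method: "All study PTs will follow the Brief Action Planning approach". DI participants receive an unrelated monthly newsletter until their own intervention in week 27.
- **Sample Size Calculation.** "Based on a difference of 8 points, an estimated SD of 12.4", and "a total of 102 participants (51 per group) would be needed (90% power" at a two-sided 0.05 level. Recruitment of 134 is explained by attrition alone. No ICC, cluster size or design effect appears.
- **Efficacy Analyses.** The mixed model adjusts for the baseline value and sex and tests a group-by-time interaction. An unstructured matrix "will be used to model the within-subject error variance-covariance for continuous outcomes". Sandwich standard errors are added, but the independent unit they are built on is not named. There is no PT or session term and no sensitivity analysis for clustering.

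**The concern.** PAM measures confidence in managing one's condition, which is what group education and motivational counselling try to change. Participants who shared a session or a PT may therefore resemble one another at T1 more than participants who did not. DI participants have had neither by then, so the dependence sits in one arm only (a partially nested design).

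A within-subject covariance matrix describes repeated scores from one person and says nothing about correlation between people. A sandwich estimator built on participants has the same limit. If such correlation exists, the II mean is less precise than the model believes, the confidence interval for the T1 difference is too narrow, and the test rejects too often. The sample size makes no provision for it either. If PT and session are not recorded at delivery, it may be impossible to check this later.

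**Working it through.** **1. Reproduce the plan's figure.** Inputs from Sample Size Calculation: difference 8, SD 12.4, two-sided 0.05, 90% power. Allocation is 1:1 (Study Design).

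n per group = 2 × [12.4 × (1.960 + 1.282) / 8]² = 50.5, rounded up to 51, or 102 in total. This matches the plan.

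The standard error at 51 per group is 12.4 × √(2/51) = 2.456, so the power is Φ(8/2.456 − 1.960) = Φ(1.298) = 90.3%. The stated number is fully explained by independent participants, so it contains no design effect. The recruitment margin is 1 − 102/134 = 23.9%, which is the attrition allowance.

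**2. Allow for clustering in II only.** For II clusters of average size m and intraclass correlation ρ:

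- design effect in II: DE = 1 + (m − 1)ρ
- variance factor for the T1 difference: F = (1 + DE)/2
- true level of the naive 5% test: 2 × [1 − Φ(1.960/√F)]
- power with the correct standard error: Φ(8/(2.456 × √F) − 1.960)

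**3. Put in assumed values.** The documents give neither m nor ρ. I assume m from 5 (about ten sessions among 51 analysed) to 17 (three PTs), and ρ from 0.01 to 0.05.

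| m | ρ | DE | F | Naive level | Power, unadjusted | Power, baseline correlation 0.5 |
|---|---|---|---|---|---|---|
| 5 | 0.01 | 1.04 | 1.02 | 5.2% | 89.7% | 96.1% |
| 5 | 0.05 | 1.20 | 1.10 | 6.2% | 87.4% | 94.8% |
| 10 | 0.05 | 1.45 | 1.225 | 7.7% | 83.7% | 92.5% |
| 17 | 0.01 | 1.16 | 1.08 | 5.9% | 88.0% | 95.2% |
| 17 | 0.05 | 1.80 | 1.40 | 9.8% | 78.6% | 88.9% |

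Worked row (m = 17, ρ = 0.05): DE = 1 + 16 × 0.05 = 1.80. F = 2.80/2 = 1.40. The standard error is 2.456 × 1.183 = 2.905, and the power is Φ(2.753 − 1.960) = 78.6%.

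The last column multiplies the SD by √(1 − 0.5²). The correlation of 0.5 is an assumption, and ρ is taken on the adjusted scale. Without clustering, the same adjustment gives 96.4%. The naive-level column does not change with adjustment.

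**4. Cost of few clusters.** The power figures above use a normal reference. With Satterthwaite degrees of freedom (II contributing 51/m − 1) and no baseline adjustment, ρ = 0.05 gives:

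- m = 5: 27.4 df, power 85.0%
- m = 10: 11.3 df, power 76.6%
- m = 17: 4.8 df, power 59.1%

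The choice of cluster therefore matters for any remedy.

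**The case against.** **The size is unknown and may be trivial.** This stands. At m = 5 and ρ = 0.01 the level is 5.2% and power 89.7%. A common counselling approach, participant-set goals and the large app and Fitbit component could all keep the ICC low. They do not show that it is zero.

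**Baseline adjustment is planned, so the trial is not underpowered.** This largely stands. A reader might infer that true power is below 90%. The documents do not support that: at an assumed baseline correlation of 0.5, power exceeds 90% in every row of the table except the last. Adjustment does not repair a standard error that omits between-participant correlation.

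**Inflated type I error is not a given.** This stands in part. If the intervention does nothing for anyone, treatment creates no PT clustering. If inference is confined to this trial's own PTs, treated as fixed, the usual test is sound: a simulation with three fixed PTs, 17 participants each and 5% of the variance between PTs gave a level of 4.9%. The inflated levels apply when PTs or sessions are regarded as a sample from a wider population, or when members of a session influence each other.

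**The planned test is a group-by-time interaction, not a T1 difference.** This also stands. PT effects that persist in II to T2 would partly cancel in an interaction, and DI has been treated by T2. The factors above apply to the T1 contrast and do not carry over directly to the interaction.

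**T1 and the DI education session both fall in week 27.** The order is not stated. DI calls start only in week 29, so the asymmetry holds in substance.

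**Conclusion.** The structural point holds. Group sessions and PTs are shared in II before T1 and not in DI, the model represents only within-subject correlation, and the 51 per arm carries no design effect. If outcomes correlate within session or PT, the T1 standard error is understated. The sandwich estimator does not answer this unless its unit is the session or PT, and even then it would need a small-sample correction when clusters are few.

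The size cannot be fixed from the documents. Over the assumed range (clusters of 5 to 17, ICC 0.01 to 0.05), the variance factor is 1.02 to 1.40, the naive level about 5.2% to 9.8%, and unadjusted power about 79% to 90% by normal approximation.

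Two stronger readings are not supported: that the type I error certainly exceeds 5%, and that power is certainly below 90%. Nor does the evidence require a PT random effect in the primary analysis, because with few PTs that choice could cost far more power than the clustering itself. This is a cheap improvement, not a flaw that invalidates the design.

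**What to change.** - Record the PT and the education session for each participant at delivery, in both arms.
- Prespecify a sensitivity analysis of the T1 contrast that is partially nested: a random session effect in II, DI participants as singletons, and Satterthwaite or Kenward-Roger degrees of freedom. Report the estimated ICC.
- For T2, include the cluster term in both arms and allow PTs to be crossed with arm, since the same PT may treat both.
- Name the independent unit of the sandwich estimator.
- In Sample Size Calculation, state that 90% power assumes independent participants. Give the expected number of PTs and session size, and show power over a range of ICCs.

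The cost is two ID fields, one extra model and a wider interval. The interval could be much wider if PT is the cluster and there are few PTs (about 59% unadjusted power with three PTs and ICC 0.05). Session is therefore the preferred cluster, and PT-level results should be labelled supportive only.

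### The delayed group sets its first activity goals on an entry readiness screen that is 27–28 weeks old; repeating the PAR-Q at T1 is a cheap safety improvement

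*Combined protocol and SAP*

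**What the plan says.** The Participants section uses the PAR-Q as an entry screen: "We will exclude people who should not be physically active without medical supervision, as identified by the Physical Activity Readiness Questionnaire (PAR-Q". For those who fail it, a physician's "note will be required to determine if they are eligible". The PAR-Q is named nowhere else in the plan. Fig 1 has one mark in its Eligibility row, under Enrolment at weeks −1 to 0, and no row for the PAR-Q itself.

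The II group has its education session in week 1. That session includes individual physiotherapist (PT) counselling in which "participants will be guided to set their own physical activity goals, develop an action plan, and identify barriers and solutions". II participants then get "a phone call from their PTs at weeks 2, 4, 6, 8, 13 and 26".

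For the other arm, The Intervention section says "The DI group will receive the same intervention in week 27". Fig 1 agrees: education session at week 27, then "PT Phone Calls (Weeks 29-52". Until then DI participants receive a monthly newsletter that does not deal with managing the disease.

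Fig 1 lists seven assessments at T1: PAM, RADAI, FSS, MPQ-SF, PHQ-9, SRHI and SenseWear. None is a readiness screen. Adverse Events and Data Monitoring adds a Month 6 question about serious adverse events, direct reporting of such events to the coordinator at any time, and committee review.

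**The concern.** The PAR-Q is there to protect people who are about to become more active. In II it does that job just before the programme starts. In DI the programme starts about half a year after the screen, and nothing in the plan asks whether the answers still hold.

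If the plan is followed exactly, a DI participant whose PAR-Q answers have changed since entry can begin setting activity goals without the physician's note that the same answers would have triggered at entry. A changed answer need not be a serious adverse event, so the Month 6 question may not catch it. What is at stake is equal protection for the two arms at the start of the programme, not the validity of the efficacy result.

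**Working it through.** **The plan's own figures.** The plan states no age for the PAR-Q answers. The only planning figures used here are in Sample Size Calculation, and they reproduce.
- Per group: 2 × (1.960 + 1.282)² × 12.4² / 8² ≈ 50.5, rounded up to 51, so 102 in total as stated.
- Attrition implied by recruiting 134: 1 − 102/134 = 23.9%, against the stated ~24%.

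**Age of the screen.** Age = week of the contact − week of the eligibility check (0 or −1, from Fig 1).

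| Contact | II | DI |
|---|---|---|
| First goals (education session) | week 1: 1 − 0 = 1 to 1 − (−1) = 2 weeks | week 27: 27 − 0 = 27 to 27 − (−1) = 28 weeks |
| Last PT call | week 26: 26 to 27 weeks | week 52: 52 to 53 weeks |

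In days, first goals are set 7–14 days after the screen in II and 189–196 days after it in DI. For anyone who failed the PAR-Q and entered on a physician's note, the clearance of that age is mainly the note.

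**People concerned.** At most 67 in DI; with 24% attrition, 67 × 0.76 ≈ 51.

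**New failures.** The documents give no rate. For scale only, one expected new failure corresponds to a rate of 1/67 = 1.5% or 1/51 = 2.0%. This counts screen failures, not harm.

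**What already covers the gap.**

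| Safeguard in the plan | Re-screens readiness? | Can hold the start? |
|---|---|---|
| Individual PT counselling at the session | No instruction to do so | None stated |
| Month 6 serious-event question | No, asks about events | None stated |
| Any-time reporting of serious events | No | None stated |
| Committee review of events and screening documents | No | May recommend ending the study; no individual hold stated |

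**Efficacy.** DI is unexposed until week 27, so the age of the screen does not enter alpha, power, sample size or the T1 comparison.

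**The case against.** The case against has real weight.

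- **No expiry is stated.** The plan gives no validity period for the PAR-Q, so nothing in it shows that 27–28 weeks is too old. This stands: treating the screen as stale is a judgement.
- **II screens age too.** At the week 26 call the II screen is 26–27 weeks old, and goals may still be modified then. This also stands as a fact. The difference is that II participants set their first goals on a fresh screen and are in regular PT contact afterwards, whereas the plan gives DI no PT contact or app access before week 27. Separating first goals from modified goals is the reviewer's distinction, not the plan's.
- **DI participants do not start alone.** DI gets the same one-to-one session, and the PT's role is to "guide the user in setting realistic physical activity goals". RADAI, pain, fatigue and mood are collected at T1, and usual medical care continues. The PT session is a substantial safeguard. Still, no text tells the PT to ask about readiness or to wait for a note, or says that the PT sees the T1 scores.
- **The single timing is inferred.** Correct: it follows from the PAR-Q being an eligibility criterion and from the single Eligibility mark.

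A reader might infer that the plan breaks its own exclusion rule. It does not. Participants states a condition for entry, not a continuing one. A reader might also extend the point to the six-month criteria on joint surgery and injury. The plan gives those no safety rationale and no physician's-note route, so they are not part of this point.

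**Conclusion.** The point holds as a minor, inexpensive safety improvement. DI first goals rest on a readiness screen 27–28 weeks old, against 1–2 weeks in II, for up to 67 people (about 51 at planned attrition). Existing safeguards reduce the risk, but none repeats the screen or holds a start.

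This rests on two things: that the PAR-Q is done when Fig 1 marks eligibility, and that absence of any re-check in the text means none is planned.

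A reader might go on to infer that DI participants are being put in danger or that the result is compromised. The documents support neither. They give no rate of new failures and no link from a failure to harm, DI goals are set with a PT present, and the efficacy inference is untouched.

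**What to change.** After T1 measurement, including the 7-day SenseWear wear, and before the DI education session, repeat the PAR-Q for DI participants. Add the row to Fig 1 at T1 for DI. Require a physician's note, and hold activity goal setting until it arrives, only when an answer is newly positive since entry or is not covered by an existing note. Participants cleared at entry whose answers are unchanged proceed; applying the rule to every failure would hold them for no gain. Keep everyone in intention-to-treat follow-up to T2 whatever the result.

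**Cost.** It is a small amendment that reuses one questionnaire and one rule.
- *Timing.* Fig 1 puts T1 and the DI session in the same week, so there is little slack. A participant waiting for a note may need a make-up session. Assuming a 2–4 week wait, 24/26 = 92% to 22/26 = 85% of the programme weeks before T2 (53 − 27 = 26) remain.
- *T2 data.* Late starts may slightly dilute the DI results at T2, which Efficacy Analyses includes. As an illustration, not a bound: if the planning effect of 8 points holds in DI, each participant who received none of it would lower the DI T2 mean PAM by 8/67 = 0.12 to 8/51 = 0.16 points. Divided by the SD of 12.4, that is 0.010 to 0.013 SD. With 51 participants and an assumed effect of 4 to 12 points, the figure is 0.08 to 0.24 points.
- *T1 data.* These are unaffected, because they are collected before the re-check.
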